7.1.1.9 Interactive Voice Response System/Integrated Web Response System

The investigator or designee will call/log into IVRS/IWRS as specified in the Trial Flow Chart. Upon confirmation of a subject's eligibility at Visit 2, the investigator or designee will call IVRS or log into IWRS to randomize the subject. Subjects who do not meet eligibility criteria at Visit 4 will be screen-failed in IVRS/IWRS. For all randomized subjects, the investigator or designee will continue to call/log into IVRS/IWRS as per the Trial Flow Chart. For completed or discontinued subjects, the investigator or designee will make the final call/web action into IVRS/IWRS at their last trial visit. For additional information, please refer to Section 5.3.

7.1.2 Clinical Procedures/Assessments

7.1.2.1 Physical Assessments/Examinations

7.1.2.1.1 Neurological Examination (Neuro Exam)

A complete physical examination (PE), including a neurological exam, will be performed by a primary investigator or sub-investigator. This examination will also be performed in the event of early discontinuation. The following body systems should be included in these exams:

7.1.2.1.3 Vital Signs

Body Temperature: Body temperature will be measured with an oral or tympanic thermometer. The same method (e.g., oral, or tympanic, °C) should be used for all measurements for each individual subject and should be the same for all subjects throughout the trial.

Heart Rate (HR), Blood Pressure (BP) and Respiratory Rate (RR): Subjects should be resting **for at least 10 minutes** prior to having vital sign measurements obtained. The **same position** should be used for all measurements for each individual subject and should be the same for all subjects throughout the trial. The correct size of the blood pressure cuff and the correct positioning on the subject's arm is essential to increase the accuracy of blood pressure measurements. The same method (e.g., manual, or automated) should be used for all measurements for each individual subject and should be the same for all subjects throughout the study.

Vital signs will be assessed also after the tSCS sessions for identifying any adverse effect.

7.1.2.1.4 Body Height/Weight

Height (cm/in) and body weight (kg/lbs.) will be collected and recorded. Measurements should be recorded to the nearest centimeter/inch and kilogram/pound. Body weight data will be collected without shoes and with heavy clothing (such as coats) removed. Body weight should be performed on the same scale for the same individual throughout the study.

7.1.2.2 Neurological and Cognitive exam

At baseline and by end of the visit 2 (stimulation) a neurological exam (as defined in section 12.6) will be administered for identifying CNS related adverse events.

7.1.2.2.2 Measurements of Upper-Limb Function

The Nine-hole peg test (9HPT) has been validated as the assessment of the hand function for MS⁴⁶, with 15 to 20% defined as the minimal clinically important difference. In order to capture the upper-limb functioning we will include the Action Research Arm Test for motor function. The smallest real difference/minimal detectable change is defined as 5.7 points for the ARAT54 and 5.5 points for the Box and Blocks Test in stroke55. The Asworth scale will be used for assessing spasticity and the NeuroQOL Upper Extremity function as a PRO relevant for upper-limb dysfunction. In addition we will include a validated scale for fatigue in MS such as the MFIS and a global scale such as GIC for identifying additional effects of PROs.

7.1.3 Laboratory Procedures/Assessments

No laboratory procedures are planned.

7.1.4 Other Procedures

7.1.4.1 Withdrawal/Discontinuation

When a subject discontinues/withdraws from participation in the trial during visit 2 (before completing the three planned stimulations), all applicable activities scheduled for the end of visit 2, as outlined in Section 6.0 Trial Flow Chart, will be performed at the time of discontinuation. Any adverse events which are present at the time of discontinuation/withdrawal will be followed in accordance with the safety requirements outlined in Section 7.2 - Assessing and Recording Adverse Events

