5.8 Subject Withdrawal/Discontinuation Criteria

Subjects may withdraw consent at any time for any reason or be dropped from the trial at the discretion of the investigator should any untoward effect occur. In addition, a subject may be withdrawn by the investigator if enrollment into the trial is inappropriate, the trial plan is violated, or for administrative and/or other safety reasons. Specific details regarding discontinuation or withdrawal procedures are provided in Section 7.1.4 – Other Procedures.

[Table 1](#) provides reasons why a subject must be discontinued from treatment but may continue to be monitored in the trial, as well as reasons why a subject must be discontinued from treatment and the trial.

Table 1 Discontinuation Scenarios

Reason for Discontinuation Scenario	Action
The subject or legal representative (such as a parent or legal guardian) withdraws consent.	Discontinuation from Treatment and Trial
The subject has a medical condition or personal circumstance which, in the opinion of the investigator, places the subject at unnecessary risk through continued participation in the trial or does not allow the subject to adhere to the requirements of the protocol.	Discontinuation from Treatment and Trial
The subject is no longer able to participate in the trial or is not compliant with trial-related procedures.	Discontinuation from Treatment and Trial
The subject takes a prohibited treatment during the trial.	This deviation should be documented and consulted regarding the management of the subject.
Subjects who report suicidal ideation with intent, with or without a plan or method (i.e., a positive response to items 4 or 5 in the assessment of suicidal ideation on the C-SSRS) or suicidal behavior may meet discontinuation criteria.	Please refer to Section 7.1.2.2.11, 7.2.3.2 and the ECI guidance document for details.

Discontinuation from treatment is “permanent.” Once a subject is discontinued, he/she shall not be allowed to restart treatment.

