7.1.5.1.2 Visit 2: Baseline

Patients will be randomized to either treatment or sham stimulation and assigned a code. Before starting stimulation, the researcher will conduct a vital signs and neurological examination. Then, the patient will be subjected to the first tSCS stimulations (a 30 min stimulations).

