8.0 STATISTICAL ANALYSIS PLAN

8.1 Statistical Analysis Plan Summary

Linear mixed-effects models will be used to test the association between treatment arm and all primary and secondary endpoints. These models will include an outcome measure as the dependent variable, treatment assignment, time of measurement, and their interaction as independent variables and a random intercept for participant and site to account for the longitudinal and clustered nature of the data. If imbalances exist in baseline characteristics between treatment groups, sensitivity analyses will be conducted by including the covariate in the mixed-effects models as an independent variable to determine the impact it may have on the desired association. For the primary outcome, the interaction between treatment assignment and the 6 weeks follow-up will be assessed, with statistical significance indicating a difference in the change in 9-HPT is present between treatment groups at V5. All other time points and outcome measures will be treated as secondary. These analyses will be conducted following the intention to treat principle. Additional exploratory analyses will be conducted on the per protocol population defined as those who completed at least 70% of therapeutic sessions.

Table 4 Statistical analysis plan

Study Design Overview	Transcutaneous Electrical Spinal Stimulation (tSCS) for Improving Upper Limb Function in People with MS
Treatment Assignment	Active stimulation: tSCS Sham: stimulations using a non-active electric stimulation
Analysis Populations	Intention to treat Per Protocol
Primary Endpoint(s)	Differences in the nine-hole peg test (9-HPT) affected hand in the tSCS treated vs. sham groups by the end of treatment (V3 vs V5)
Key Secondary Endpoints	1. Percentage of responders: 20% difference on the 9HPTd (minimal clinically important difference (MCID)) from baseline to end of the study 2. Change in the 9HPT dominant and non-dominant hand from baseline to end of the study 3. Change in the Action Research Arm Test (ARAT) from baseline to end of the study 4. Change in the modified Ashworth Scale (mAS) for spasticity assessment from baseline to end of the study

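### After Visit 2, a participant who discontinues is owed neither a 9HPT nor follow-up to V5, so obtainable primary-endpoint values may be lost

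*Protocol*

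**What the plan says.** Section 5.8 refers the reader to Section 7.1.4 for discontinuation procedures. The rule there opens "When a subject discontinues/withdraws from participation in the trial during visit 2". A bracket limits it further to a subject who has not yet had all of three intended stimulations. Such a subject is to have, on leaving, whatever the flow chart lists for the close of Visit 2.

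Section 7.1.5.1.2 describes Visit 2 as the randomization visit: "Then, the patient will be subjected to the first tSCS stimulations (a 30 min stimulations"). The flow chart (Section 6.0) puts it on Day 42, lists double-blind assessments on Days 42, 61 and 84, and has no early-termination column.

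Two other places bear on early stopping:

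- Section 7.1.2.1.1, on the physical and neurological examination, adds: "This examination will also be performed in the event of early discontinuation".
- The lead-in to Table 1 (Section 5.8) says that the table gives "reasons why a subject must be discontinued from treatment but may continue to be monitored in the trial". One row then reads "The subject is no longer able to participate in the trial or is not compliant with trial-related procedures", with the action of ending both treatment and trial.

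On the analysis, Section 8.1 tests the treatment-by-time interaction at the 6-week follow-up (V5) in a linear mixed model with random intercepts for participant and site. It says: "These analyses will be conducted following the intention to treat principle". A per-protocol analysis of those with at least 70% of sessions is exploratory.

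**The concern.** The discontinuation rule appears to be written for a trial in which all stimulation happens at one visit. Here treatment lasts six weeks, so most of the time in which a participant can stop lies outside the rule.

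The primary test turns on the V5 value of the 9HPT. If sites follow the text, a participant who stops in week three can leave with no 9HPT at that point and no invitation to V5. Someone judged non-compliant is taken out of the trial altogether. An intention-to-treat analysis needs the outcomes of exactly these people. Losing them moves the observed V5 data towards the per-protocol set, which the plan treats as exploratory. An analysis plan can choose how to handle missing values, but it cannot recover values that were never measured.

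**Working it through.** **1. Does any provision require a 9HPT or V5 follow-up after a later stop?**

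| Place | What it requires | 9HPT after a later stop? |
|---|---|---|
| Section 7.1.4.1 | End-of-Visit-2 activities, for withdrawal during Visit 2 | No |
| Section 7.1.2.1.1, with the examination in Section 12.3 | Physical and neurological examination at early discontinuation | No; the modules contain no 9HPT |
| Table 1, lead-in | Foresees monitoring after treatment stops | Not stated |
| Table 1, rows | Three end treatment and trial; two refer the case elsewhere | No row assigns continued monitoring |
| Section 6.0 | Scheduled visits only | No early-termination column |
| Section 7.1.5.1.3 | 9HPT on the last stimulation day of each session period | Silent on those who have stopped |

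No provision requires it, and none forbids it. I read V5 as Day 84, because Section 8.1 ties V5 to six weeks of follow-up and 42 + 42 = 84.

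**2. The plan's sample size (Section 8.9).** Inputs: d = 0.8, SD 5.5, two-sided 0.05, 26 per arm, 15% attrition, 60 enrolled.

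- Difference: 0.8 × 5.5 = 4.4, as stated.
- Power of the two-sample t-test (noncentral t) at 26 per arm: 80.7%. The stated figure of greater than 80% reproduces, and 26 is the smallest number per arm that reaches 80%.
- Enrolment: 52 / 0.85 = 61.2, so 62; 52 × 1.15 = 59.8, so 60. The planned 60 is close enough for this point.

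**3. How many V5 values could be missing.** The synopsis gives 10% attrition and Section 8.9 gives 15%.

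- 10%: 60 × 0.10 = 6 missing, 54 left, power 82.2%.
- 15%: 60 × 0.15 = 9 missing, 51 left (26 and 25), power 79.9%.
- None missing, effect unchanged at d = 0.8: power 86.1%.

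These counts are upper figures for each rate. They assume that all attrition falls between randomization and V5 and that nobody who stops is assessed at V5.

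**4. Possible bias.** Assume, for illustration only, that active-arm leavers keep none of the 4.4-unit benefit and that completers show all of it. With a fraction f leaving, the intention-to-treat difference is 4.4 × (1 − f).

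| f | Intention-to-treat difference | Overstatement by completers | Power with all 60 followed |
|---|---|---|---|
| 5% | 4.18 | 0.22 | 82.5% |
| 10% | 3.96 | 0.44 | 78.3% |
| 15% | 3.74 | 0.66 | 73.6% |

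The last column shows that fuller follow-up is not a route to more power under this assumption. At 15%, 73.6% is below the 79.9% from 51 completers at the full effect. What follow-up gains is an estimate of the difference that an intention-to-treat analysis is meant to measure.

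**The case against.** Several stronger readings are tempting, and the protocol does not support them.

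- *A reader might infer that nothing is assessed after a later stop.* The physical and neurological examination is required at early discontinuation, without restriction to Visit 2. What is not required is the 9HPT.
- *A reader might infer that later leavers certainly have no end-of-treatment 9HPT.* The text is silent rather than prohibitive. The lead-in to Table 1 foresees continued monitoring, and the flow chart does not exempt people who have stopped treatment from scheduled assessments.
- *A reader might infer that leavers fall out of the analysis and that intention to treat is only a label.* The mixed model keeps a leaver's baseline and any Day 61 9HPT. Only the V5 value is missing, and the model handles it under missing at random. Sensitivity analyses for missing data commonly belong in an analysis plan that is not shown here, and their absence is not part of this point.
- *A reader might infer that dropout will differ by arm.* That is possible: Section 3.4 names adverse events and lack of efficacy among the reasons to be recorded. It is not shown. The protocol calls the stimulation well tolerated, offers sham participants active treatment afterwards, and reimburses travel.
- *A reader might take nine lost values as expected.* Section 8.9 calls 15% conservative and cites 10% in a previous trial. A six-week run-in precedes randomization, so some attrition among those enrolled may come before it.

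Some loss is also unavoidable. No protocol rule can obtain a value from a person who withdraws consent, and often not from one who can no longer take part. The clearest avoidable loss is from the non-compliance clause.

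These points narrow the concern without removing it. The stated rule does not fit the treatment period, and which outcomes sites collect after discontinuation is a protocol procedure.

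**Conclusion.** The point holds as a gap in outcome collection. Section 7.1.4.1 is worded for a single stimulation visit. For a stop later in the six weeks, the protocol requires neither a 9HPT nor follow-up to V5. Table 1 takes non-compliant participants out of the trial, although its own lead-in foresees continued monitoring.

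The consequence is that up to 6 (10% attrition) or 9 (15%) of 60 V5 values may be missing, some of them obtainable, and that the primary analysis must rely on missing at random for them. Power is not the main issue, at about 80% to 82% on the remaining 51 to 54. The possible bias is 0.66 units on a target of 4.4 at 15% leaving. That figure rests on the assumption that active-arm leavers keep no benefit and on using completers alone. Interim 9HPT values could let the mixed model correct part of it, and a different pattern of leaving in the sham arm could change its size or direction. The figure shows scale and is not a forecast.

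**What to change.** Reconcile Sections 5.8 (Table 1), 6.0, 7.1.2.1.1, 7.1.4.1 and 7.1.5.1.3 so that they state the following:

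1. Participants who stop treatment or are non-compliant, and who have not withdrawn consent, stay in the trial for outcome assessment and are still invited to the scheduled V5 (Day 84) 9HPT. This is the more important half, because only a V5 measurement supplies the primary outcome.
2. For those who leave the trial at any time up to Day 84, the 9HPT and the other end-of-treatment assessments are done at discontinuation where the participant agrees. They are recorded as an early-termination value and not as V5.
3. The flow chart gains an early-termination column that matches these rules.

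This concerns the collection of outcomes only. It does not touch when or why treatment should be stopped. The cost is a change of wording and about six to nine assessments at most, with V5 already on the schedule.

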7.1.4.2 Blinding/Unblinding

When the investigator or sub-investigator needs to identify the treatment arm used by a subject in case of emergency e.g., the occurrence of serious adverse experiences, he/she will contact the emergency unblinding call center by telephone and make a request for emergency unblinding. As requested by the investigator or sub-investigator the emergency unblinding call center will provide the information to him/her promptly and report unblinding. The emergency unblinding call center will make a record promptly however, the investigator or sub-investigator must enter the intensity of the adverse experiences observed, their relation to study arm, the reason thereof, etc., in the medical chart etc., before unblinding is performed. Additionally, the investigator must go into the IVRS system and perform the unblind in the IVRS system to update arm disposition. If the emergency unblinding call center is not available for a given site in this trial, IVRS/IWRS should be used for emergency unblinding in the event that this is required for subject safety.

If unblinding has occurred, the circumstances around the unblinding (e.g., date and reason) must be documented promptly, and principal investigator notified as soon as possible. Only the principal investigator or delegate and the respective subject's code should be unblinded. Trial site personnel directly associated with the conduct of the trial should not be unblinded.

7.1.4.3 Domiciling

NA

7.1.4.4 Calibration of Critical Equipment

Not required for the SCONE device.

7.1.5 Visit Requirements

Visit requirements are outlined in Section 6.0 - Trial Flow Chart. Specific procedure-related details are provided above in Section 7.1 - Trial Procedures.

7.1.5.1 Visits

Each visit should be performed as noted in the Trial Flow Chart. For visits that require additional explanations, please see those specific visits below.

7.1.5.1.1 Visit 1: Screening

At Visit 1, subjects who provide informed consent will undergo a series of diagnostic and safety assessments to determine if they are eligible for the trial. A designated subject must also consent to participate and will be asked to complete certain assessments throughout the trial. Subjects planning to undergo elective procedures during the study (known prior to trial start) should not proceed until such procedures have been completed.

At the screening visit, medical history, use of drugs, alcohol, caffeine, smoking will be recorded. If the subject fulfills the inclusion criteria and signs the informed consent, the patient will then be exposed to a 6-week run-in period with standard occupational therapy.

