1.0 TRIAL OUTLINE

Study Title	Transcutaneous Electrical Spinal Stimulation (tSCS) for Improving Upper Limb Function in People with MS
Study Registration	TBD
Study Category	Interventional
Phase	Pilot study
Background & Rationale	The ability to efficiently use their hands is critical for maintaining activities of daily living (ADLs), a crucial unmet need for people with MS (PwMS). Recent clinical trials in patients with spinal cord injury have shown excellent safety and provided evidence of efficacy that tSCS associated with occupational therapy can improve the upper limb (UL) function and the ability to perform ADLs. Therefore, we propose to test the efficacy of tSCS in a pilot study in PwMS with moderate to severe UL disability.
Study Design	Double-blind, parallel, randomized, two arms, sham-controlled study in patients with MS and with significant disability of the upper limbs treated with tSCS and occupational therapy
Objective(s)	To assess the safety and efficacy of tSCS as add-on to standard rehabilitation in MS patients with moderate to severe UL disability
Outcome(s)	
 Primary endpoint: differences in the nine-hole peg test (9-HPT) affected hand in the tSCS treated vs. sham groups by the end of treatment (V3 vs V5) Secondary endpoints: 
 Percentage of responders: 20% difference on the 9HPTd (minimal clinically important difference (MCID)) from baseline to end of the study Change in the 9HPT dominant and non-dominant hand from baseline to end of the study Change in the Action Research Arm Test (ARAT) from baseline to end of the study Change in the modified Ashworth Scale (mAS) for spasticity assessment from baseline to end of the study Hand strength measured by Grip and Pinch force dynamometers from baseline to end of the study Change in the NeuroQOL Upper Extremity function from baseline to end of the study Change in the Modified Fatigue Impact Scale (MFIS) from baseline to end of the study

	
9. Change in Global Impression of change (GIC) from baseline to end of the study
 
Safety and Tolerability
 
 1. presence of serious adverse events 2. Retention rate 3. % sessions attended
Inclusion / Exclusion Criteria	
Inclusion: Patients with MS and moderate to severe UL disability defined as 9HPT affected hand ≥ 33.4 sec; 21 to 65 years old
 
Exclusion: patients with relevant comorbidities, pacemakers or metal implants

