5.1.2 Subject Inclusion Criteria

In order to be eligible for participation in this trial, the subject must:

1. Be between 21 to 65 years of age (inclusive) on the day of signing informed consent.
2. Have MS (McDonald criteria 2017) with moderate to severe upper-limb disability defined as 9HPT in the dominant hand/functional hand > 33.3 sec (range: 33.3-240 sec)
3. Any type of disease modifying therapy is allowed and should be stable in the last 3 months.
4. Not having received corticosteroids previous month.
5. Each subject must sign the informed consent form, in accordance with local requirements, after the scope and nature of the investigation have been explained to the subject, and before Screening assessments.
6. Based on the investigator's judgment, the subject should:
 - a. Be able to speak, read, and understand the language of the trial staff and the informed consent form;
 - b. Possess the ability to respond verbally to questions, follow instructions, and complete study assessments.
 - c. Be able to adhere to the stimulation protocol and visit schedules.
7. Women of child-bearing potential* must have a negative urine pregnancy test before the inclusion in the study and agree to use highly effective contraceptive methods during the study. Highly effective contraceptive methods will include intrauterine device, implant, patch or pill, bilateral tubal occlusion, vasectomized partner and sexual abstinence.

* A woman will be considered of childbearing potential, following menarche and until becoming post-menopausal unless permanently sterile. Permanent sterilization methods include hysterectomy, bilateral salpingectomy and bilateral oophorectomy. A postmenopausal state is defined as 0 menses for 12 months without an alternative medical cause. A high follicle stimulating hormone level in the postmenopausal range may be used to confirm a post- menopausal state in women not using hormonal

contraception or hormonal replacement therapy. However, in the absence of 12 months of amenorrhea, a single follicle stimulating hormone measurement is insufficient.

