6.0 TRIAL FLOW CHART

Table 2 Trial flow chart

Visit Number	1	2	3-6	7
Visit Title	Screening	Randomization Baseline	Double blinded assessment	OLE

Scheduled Week/Day	Day 0	Day 42	Days 42-61-84	Day 126
Scheduling Window by Days:	±2	±3	±3	±5
Administrative Procedures				
Informed Consent – Subject	X			
Inclusion/Exclusion Criteria	X			
Subject Identification Card	X			
Medical History	X			
Prior Medication Review	X			
Randomization		X		
Monitor Trial Device Compliance		X		
Clinical Procedures/Assessments				
9HPT		X	X	X
ARAT		X	X	X
mAS		X	X	X
NeuroQOL		X	X	X
MFIS		X	X	X
GIC		X	X	X
Safety		X	X	X

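### The eligibility schedule contradicts itself: the run-in gate at Visit 1 needs a 9HPT time that is first scheduled at Visit 2, and one sentence screen-fails patients at Visit 4, after randomisation

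*Protocol*

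**What the plan says.** - **The criterion.** Inclusion criterion 2 in section 5.1.2 requires "9HPT in the dominant hand/functional hand > 33.3 sec (range: 33.3-240 sec"). Section 5.1.1 repeats it. The synopsis in section 1.0 words it differently: "moderate to severe UL disability defined as 9HPT affected hand ≥ 33.4 sec; 21 to 65 years old".
- **The gate.** Section 7.1.5.1.1 says that consenting subjects at Visit 1 "will undergo a series of diagnostic and safety assessments to determine if they are eligible for the trial". It then states: "If the subject fulfills the inclusion criteria and signs the informed consent, the patient will then be exposed to a 6-week run-in period".
- **What is recorded at Visit 1.** The same section lists: "At the screening visit, medical history, use of drugs, alcohol, caffeine, smoking will be recorded". It does not name the 9HPT.
- **The flow chart (section 6.0).** The "Inclusion/Exclusion Criteria" row is marked at Visit 1 (Day 0) and nowhere else. The 9HPT row is empty at Visit 1 and marked at Visit 2 (Day 42), Visits 3-6 and Visit 7. Randomisation is marked at Visit 2.
- **The randomisation system (section 7.1.1.9).** A subject is randomised once eligibility has been confirmed at Visit 2. The next sentence reads: "Subjects who do not meet eligibility criteria at Visit 4 will be screen-failed in IVRS/IWRS".
- **Failing the criteria (section 7.1.1.2).** A subject found not to meet the criteria is withdrawn. The visits at which this applies are not named.

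**The concern.** The 9HPT time is what defines moderate to severe upper-limb disability in this trial, so the visit at which it is measured and applied decides who enters. Six weeks of occupational therapy separate Visit 1 from Visit 2. A patient can be inside the range on one day and outside it on the other, so the two visits can define different populations. Patients are recruited at three hospitals in Barcelona and one centre in the Netherlands. If the text supports more than one reading, these centres can apply different entry rules.

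The Visit 4 sentence raises a separate problem. Screen failure is a status before randomisation. Applied after randomisation, it would take randomised patients out of a trial that section 8.1 analyses by intention to treat. Section 5.9 intends no replacement, so each such removal would also come off the planned 60.

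**Working it through.** The point turns on the order of events and not on a calculation, so the sections are set side by side.

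1. **What the gate needs.** Entry to the run-in requires the inclusion criteria to be met (7.1.5.1.1). Criterion 2 is a 9HPT time (5.1.2). The gate therefore needs a 9HPT value before the run-in starts.

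2. **What the schedule supplies.** The criteria are checked on Day 0 and the first 9HPT is on Day 42 (6.0). 42 - 0 = 42 days, or 6 weeks, which is the length of the run-in. The measurement is scheduled at the end of the period that it is meant to open.

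3. **Whether other text fills the gap.** Section 7.1.5.1 says each visit is performed as the flow chart shows. Section 7.1 allows unscheduled procedures only when the investigator judges them clinically necessary. Neither schedules a 9HPT at screening.

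4. **Which visit decides eligibility.**

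| Section | Visit |
|---|---|
| 6.0 flow chart | Visit 1 |
| 7.1.5.1.1 | Visit 1 |
| 7.1.1.9, randomisation | Visit 2 |
| 7.1.1.9, screen failure | Visit 4 |
| 7.1.1.2 | not named |

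Three different visits are named. No section says whether the 9HPT range must hold at Visit 1, at Visit 2 or at both.

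5. **Where Visit 4 falls.** Sections 6.0, 7.1.1.9 and 7.1.5.1.2 all place randomisation at Visit 2, and the last of these also gives the first stimulation there. The flow chart puts Visits 3-6 in the double-blind period. Visit 4 is therefore after both randomisation and the start of treatment.

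6. **Whether the criterion is stated once.** The synopsis uses the affected hand, at least 33.4 s, with no upper limit. Sections 5.1.1 and 5.1.2 use the dominant/functional hand, above 33.3 s, with a range up to 240 s. If times are recorded to 0.1 s (an assumption), the two lower limits coincide, because the first value above 33.3 is 33.4. The hand and the upper limit still differ. The range as printed also starts at 33.3 s, a value that the strict inequality excludes.

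7. **Effect on the sample size.** Section 8.9 uses a difference of 4.4 and a standard deviation of 5.5, so d = 4.4/5.5 = 0.8. With 26 per arm and two-sided alpha 0.05, the t-test has 80.7% power, which agrees with the stated figure of more than 80%. Eligibility timing does not enter this calculation.

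**The case against.** The strongest reply is that the protocol already implies a 9HPT at screening. The gate cannot be passed without one, and Visit 1 includes unspecified assessments for eligibility. The flow chart is also incomplete in general: it has no rows for vital signs, the neurological examination, grip and pinch force or the pregnancy test, all of which other sections call for. This part stands. The defect is a test that the text implies and the schedule omits, and sites may well perform it. A reader might infer that the protocol sends ineligible patients into therapy. It does not, because its own gate forbids that.

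A second reply is that the sections can be read together: the criteria must hold at Visit 1 and be confirmed at Visit 2. That reading is reasonable, but no section states it for the 9HPT range, and a site could as well treat the Visit 1 check as final.

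A third reply is that Visit 4 is a numbering slip. Section 7.1.5.1 also refers to Visits 13, 14 and 29, while the flow chart ends at Visit 7. A slip is likely. The sentence is still an operating instruction for the randomisation system and should not stand. A reader might infer that patients who improve on treatment would be removed at Visit 4. The documents do not say that the 9HPT range is re-applied there, so that is not claimed.

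**Conclusion.** The point holds as an internal contradiction. Under the written schedule the 9HPT value needed at the run-in gate is not available until the run-in is over. Eligibility is placed at Visits 1, 2 and 4, and the last of these, read literally, conflicts with the intention-to-treat analysis.

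Its size is limited. It affects who enters and whether centres apply the same rule. It leaves the sample size unchanged and, once the Visit 4 sentence is corrected, the randomised comparison too.

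Two stronger readings are not supported:

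- A reader might want to count the run-ins spent on ineligible patients. The protocol gives no failure rate. An assumed rate would also mix patients who were never eligible, whom a Visit 1 test would catch, with patients who improve during the run-in, whom it would not.
- A reader might object that change during the run-in cannot be described without a Day 0 value. No objective or endpoint concerns that change, and the run-in precedes randomisation in both arms.

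The conclusion assumes only that the empty Visit 1 cell in the 9HPT row is as the sponsor wrote it. The Visit 1 text, which does not name the test, agrees with that.

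**What to change.** - Mark the 9HPT at Visit 1 in the flow chart and name it in section 7.1.5.1.1, so that the run-in gate can be applied.
- Keep the Visit 2 value as the pre-randomisation baseline.
- Reconcile sections 6.0, 7.1.1.2, 7.1.1.9 and 7.1.5.1.1: state which visit's 9HPT decides entry, and whether the range must still hold at randomisation.
- Reconcile the hand and the limits between the synopsis and sections 5.1.1 and 5.1.2, so that one criterion is applied throughout.
- Correct or delete the Visit 4 sentence in section 7.1.1.9, so that no randomised patient can be screen-failed.

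The cost is one short test at a visit that already takes place, plus edits to the flow chart and a few sentences. No change to the sample size or the analysis model is needed.
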